Oral antihistamine administration may be considered prophylactically, at the time of initiation of treatment with alpelisib. Consultation with a dermatologist is highly recommended for better assessment and management of alpelisib-induced skin toxicity. (see also Section 6.3.2.1.2). Dermatologist consult is mandated for serious cutaneous reactions (i.e. fulfilling seriousness criteria for AE Reporting) and for severe cutaneous reactions like Stevens-Johnson-Syndrome, Toxic Epidermal Necrolysis, Erythema Multiforme, Drug Reaction with Eosinophilia and Systemic Symptoms (DRESS).		
Rash		

Worst toxicity – CTCAE Grade (value)	Dose Modifications for alpelisib
Grade 1 (<10% body surface area (BSA) with active	Maintain dose level
skin toxicity*)	 Initiate topical corticosteroids 3-4 x daily, preferred compounds to use are Triamcinolone, Betamethasone as long as skin toxicity is active, during maximum 28 days
	Add oral anti-histamine (sedative or non-sedative)
	 If active rash is not resolved within 28 days of appropriate treatment, add a low dose systemic corticosteroid (20-40 mg/d), such as prednisone 10 mg 3x/day
	For patients with symptoms like burning and/or pruritus add a non-sedating anti-histamine such as cetirizine once daily during daytime and a sedating anti-histamine such as diphenhydramine once daily a night.
Grade 2 (10-30% BSA with active skin toxicity*)	Maintain dose level
· · · · · · · · · · · · · · · · · · ·	 Initiate or intensify high potency topical corticosteroids 3-4x daily, preferred compounds to use are Triamcinolone or Betamethasone as long as skin toxicity is active, during max. 28 days
	 Add systemic corticosteroids 20-40mg/d.
	Add oral anti-histamine (sedative or non-sedative)
	If rash resolves to ≤ G1 within 10 days systemic corticosteroid may be discontinued
	For patients with symptoms like burning and/or pruritus add a non-sedating anti-histamine such as cetirizine once daily during daytime and a sedating anti-histamine such as diphenhydramine once daily a night.
Grade 3 (>30% BSA with active skin toxicity*)	Omit alpelisib dose until rash /skin toxicity is improved to Grade 1 or resolved,
	 Strongly recommend documentation by photography and performing a skin biopsy.
	 Initiate high potency topical corticosteroids 3-4x daily, preferred compounds to use are Triamcinolone or Betamethasone for at least 28 days
	Add systemic corticosteroids 20-40mg/d
	Add oral anti-histamine (sedative or non-sedative)
	 If rash resolves to ≤ G1 within 10 days systemic corticosteroid may be discontinued.
	Re-start alpelisib dose once rash /skin toxicity is fading but is no longer active (G1):
	at a reduced dose in case of first occurrence If rash/skin toxicity still active in up to 10% BSA
	after more than 14 days, continue oral

Worst toxicity – CTCAE Grade (value)	Dose Modifications for alpelisib
	corticosteroid for at least 48 hours upon re- challenge with alpelisib; if rash and/or pruritus do not reoccur within 48 hours after re-challenge with alpelisib, systemic corticosteroid may be discontinued
	For patients with symptoms like burning and/or pruritus add a non-sedating anti-histamine such as cetirizine once daily during daytime and a sedating anti-histamine such as diphenhydramine once daily at night. Antihistamine regimen should be continued for a minimum of 28 days after re-challenge with alpelisib.
Grade 4	Permanently discontinue patient from alpelisib
(any % BSA associated with extensive superinfection, with IV antibiotics indicated; life-threatening	Consult a dermatologist, strongly recommend documentation by photography and performing a skin biopsy if clinically indicated
consequences)	Treatment may follow guidelines for Grade 3 above with the exception of rechallenge.
	Additional measures may be taken as per local treatment guidance
Any Grade of Stevens-Johnson-Syndrome/Toxic Epidermal Necrolysis/Drug Reaction with Eosinophilia and Systemic Symptoms (DRESS) or other SJS/TEN/DRESS-like severe skin reactions	 Permanently discontinue patient from alpelisib treatment Consult dermatologist, strongly recommend documentation by photography and performing a skin biopsy if clinically indicated. Follow local treatment guidelines for SJS/TEN/DRESS
*"Active" skin toxicities: If there are no new lesions or ne appearance is changing color from red to pale or light b is not to be considered "active" any longer. Treatment re appearance of skin toxicity may fade slowly, over 10 da	rown, it is likely the skin toxicity has begun to fade and eduction can be considered for these areas. The
Investigations (Pulmonary disorders)	
Pneumonitis	
Please see specific instructions in Section 6.3.2.1.1	
Investigations (Metabolic)	
Asymptomatic amylase and/or lipase elevation (see	also Section 6.3.2.1.4)
Grade 1 (> ULN - 1.5 x ULN)	Maintain dose level
Grade 2 (> 1.5 - 2.0 x ULN)	Maintain dose level
Grade ≥ 3 (> 2.0 x ULN)	Omit dose until resolved to baseline, then
	If resolved in ≤ 14 days, maintain dose level
	If resolved in > 14 days, then ↓ 1 dose level
	Note:
	In cases of isolated amylase elevations only, dosing may be maintained provided amylase fractionation demonstrates that pancreatic amylase is ≤ Grade 1. Monitor total amylase (and

Worst toxicity – CTCAE Grade (value)	Dose Modifications for alpelisib	
	continue to assess fractionated amylase) as specified in Section 6.3.2.1.4	
Note: Withhold study treatment for acute onset of new or progressive unexplained abdominal symptoms, sa severe pain or vomiting; and perform diagnostic procedures (e.g., abdominal CT scan or ultrasound) to exclude pancreatic pathology.		
Investigations (any other)		
Other adverse events		
Grade 1 or 2	Maintain dose level	
Grade 3	Omit dose until resolved to ≤	
	Grade 1, then ↓ 1 dose level	
Grade 4	Permanently discontinue from alpelisib Omit dose for ≥ Grade 3 vomiting or Grade 3 nausea only if the vomiting or nausea cannot be controlled with optimal antiemetic (as per local practice)	

For additional details on the safety profile of alpelisib, please refer to the alpelisib Investigator Brochure.

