Table 6-3 Criteria for interruption and re-initiation of alpelisib treatment

Dose Modifications for alpelisib as specified below. Fulvestrant and letrozole may be continued while alpelisib dose is being held, at the investigators discretion, and as specified in Section 6.3.1

Worst toxicity – CTCAE Grade (value)

Dose Modifications for alpelisib

Investigations (Fasting Glucose or Random blood glucose)

Hyperglycemia (see also Section 6.3.2.1.3)

Consultation with a diabetologist or healthcare provider experienced in the management of hyperglycemia is highly recommended for better assessment and management of alpelisib-induced hyperglycemia. Always recommend/reinforce on lifestyle changes as per American Diabetes Association (ADA) and/or European Association for the study of Diabetes (EASD), i.e. exercise and dietary advice (e.g. controlled carbohydrate intake, high fiber, low process food intake. Three macronutrient balanced meals and 2 optional small snacks rather than one large meal).

Note: this table provides dose management recommendations. Local standard clinical practice may be followed for monitoring and managing hyperglycemia. However dose reduction should only be based on FPG. As metformin is widely available, it is an appropriate choice as initial therapy for alpelisib-induced hyperglycemia. However, SGLT2 inhibitors as per local regulations, are acceptable as well and may be administered alone or in combination with metformin. The use of metformin XR can be considered as a suitable alternative to metformin IR, alone or in combination with an SGLT2 inhibitor, particularly for participants with at least one risk factor for the development of severe hyperglycemia, at the discretion of the Investigator and as per local regulations. (Jabbour and Ziring, 2011).

Refer to Section 6.3.2.1.3 ("Guidelines for the treatment of alpelisib induced hyperglycemia") for additional details regarding the use of metformin XR and/or SGLT2 inhibitors. In case of intolerance to or unavailability of metformin, investigator's judgment should be exercised and as per local regulations, other oral anti-diabetic agents such as thiazolidinediones or dipeptidyl peptidase-4 inhibitors can be used.

SGLT2 inhibitor may increase the risk of euglycemic diabetic ketoacidosis and therefore, monitoring with serum / urine ketones and consultation with a healthcare expert experienced in hyperglycemia management or a diabetologist should be considered.

Grade 1

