FG > ULN - 160 mg/dL [> ULN - 8.9 mmol/L]

- Maintain dose level and remind participant on lifestyle changes*.
- Start/intensify metformin as per guidance below or in cooperation with a healthcare expert

Worst toxicity – CTCAE Grade (value)	Dose Modifications for alpelisib
For participants with baseline values between >ULN – 140 mg/dL (ULN – 7.7 mmol/L) this applies only for values > 140 mg/dL (7.7 mmol/L)	experienced in hyperglycemia management or a diabetologist.
	Metformin 500 mg once daily with dinner. If no gastrointestinal (GI) intolerance after several days, increase to 500 mg bid, with breakfast and dinner. If tolerated, increase to 500 mg with breakfast, and 1000 mg with dinner. If tolerated, 1000 mg bid with breakfast and dinner. If not tolerated, reduce to prior tolerated dose. Alternatively, metformin XR once daily dosing may be considered instead of metformin immediate release.
	Titrate to the MTD over a period of 3 weeks.
	 Alternatively, consider starting an SGLT2 inhibitor alone or in combination with metformin, especially in participants at risk for developing severe hyperglycemia (See Section 6.3.2.1.3 "Guidelines for the treatment of alpelisib induced hyperglycemia"). Starting dose and titration should be in accordance with the local prescribing information and consistent with local practice.
	Monitor blood glucose as clinically indicated and at least weekly for 8 weeks, then continue checking at least every two weeks until blood glucose levels are within baseline values.
Grade 2 FG > 160 - 250 mg/dL [> 8.9 - 13.9 mmol/L]	 Maintain dose level and remind patient of lifestyle changes*, exclude confounding factors like e.g. urinary tract infection, consider consultation with a healthcare expert experienced in hyperglycemia management or a diabetologist.
	Start/intensify oral anti-diabetic treatment with metformin or alternatively start an SGLT2 inhibitor alone or in combination with metformin.
	Additional oral anti-diabetic agents may be initiated, if needed. If fasting glucose levels are still rising on maximum tolerated dose of metformin or persistently > 160mg/dl (8.9 mmol/L), add an SGLT2 inhibitor if not already started, e.g. empagliflozin up to 25 mg (max. dose). Alternatively, an insulin-sensitizer, e.g. pioglitazone 30 mg (max. dose) can be added.
	 Monitor blood glucose as clinically indicated and at least twice weekly until FG resolves to ≤ Grade 1.

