	 If FPG does not resolve to ≤ Grade 1 within 21 days after institution of appropriate anti-diabetic treatment, reduce alpelisib by 1 dose level
	 Continue with anti-diabetic treatment and check fasting glucose levels at least weekly for 8 weeks, then continue checking at least every 2 weeks,

Worst toxicity – CTCAE Grade (value)	Dose Modifications for alpelisib
	alert treating physician if FG > 250 mg/dL (8.9 mmol/L) .
Grade 3	Omit alpelisib and confirm fasting status of the assessment. If non-fasting, re-check within 24 hours.
FG > 250 - 500 mg/dL [> 13.9 - 27.8 mmol/L]	Regardless of fasting status, consider IV fluids if symptoms of hyperglycemia or signs of volume depletion.
	Exclude confounding factors like e.g. urinary tract infection and consider consultation with a diabetologist.
	Administer intravenous hydration and intervention for electrolyte/ketoacidosis/hyperosmolar disturbances as clinically appropriate. Insulin may be used for 1-2 days until hyperglycemia resolves, however this may not be necessary in the majority of alpelisib-induced hyperglycemia given the short half-life of alpelisib. Start or further intensify oral anti-diabetic treatment and titrate as outlined for Grade 2.
	Monitor blood glucose as clinically indicated and at least twice weekly until blood glucose levels resolve to ≤ Grade 1.
	 If FG resolves to ≤ 160 mg/dL (8.9 mmol/L) within 3-5 days, while off study treatment and on metformin, re-start alpelisib and reduce 1 dose level, continue with anti-diabetic treatment. A second or third anti-diabetic agent maybe initiated concomitantly, if needed, in consultation with a diabetologist. Check blood glucose at least weekly for 8 weeks, then continue checking at least every 2 weeks, alert treating physician if FG>250mg/dl (13.9 mmol/L). If FG does not resolve to ≤ 160 mg/dl (8.9 mmol/L within 3-5 days while off study treatment and on metformin, consult a diabetologist for management of diabetes is strongly recommended. If FG does not resolve to ≤ 160 mg/dL(8.9 mmol/L within 21 days after institution of appropriate anti-diabetic treatment in cooperation with diabetologist and exclusion of confounding factors
	e.g. urinary tract infection, permanently discontinue patient from alpelisib treatment.
Grade 4 FG > 500 mg/dL [> 27.8 mmol/L]	 Omit alpelisib, confirm fasting status of the assessment. If non-fasting, re-check within 24 hours.
	Regardless of fasting status, consider IV fluids

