Note: Fasting plasma glucose at Day 8 and Day 15 of Cycle 1 should be performed both locally and centrally for rapid availability for safety evaluation and dose adjustments.

A central laboratory will be used for analysis of all specimens collected during the Core Phase. Details on the collections, shipment of samples and reporting of results by the central laboratory are provided to investigators in the [Laboratory Manual].

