7.2.2.5.2 Clinical chemistry

Biochemistry tests are to be performed by the central laboratory according to the schedule of assessments and collection plan outlined respectively in Table 7-1 during the Core Phase and Table 7-5. The full biochemistry panel specifics are listed in Table 7-5.

7.2.2.5.3 Monitoring fasting plasma glucose, random blood glucose, c-peptide, fasting lipid panel, amylase, lipase and HbA1C

Fasting c-peptide, amylase, lipase, HBA1C and lipid panel will be assessed by the central laboratory according to the schedule of assessments and collection plan outlined respectively

in Table 7-1 and Table 7-5 for the Core Phase. Patients must be fasting overnight for 8 to 12 hours prior to the blood draw. The study personnel will ask the patient whether she/he has been fasting, which will be captured in the eCRF as well.

Beginning with C1D8 until EOT of Core Phase, patients can have RBG testing, at the discretion of the PI.

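### The Grade 2 hyperglycemia alert line in Table 6-3 prints two glucose levels that are not equal: 250 mg/dL and 8.9 mmol/L

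*Protocol*

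**What the plan says.** Table 6-3 (Protocol, Section 6.3.1.4) sets out hyperglycemia management by CTCAE grade, with its glucose limits printed in both mg/dL and mmol/L. The Grade 2 band is "FG > 160 - 250 mg/dL [> 8.9 - 13.9 mmol/L" and the Grade 3 band is "FG > 250 - 500 mg/dL [> 13.9 - 27.8 mmol/L".

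The Grade 2 row closes with a follow-up instruction. Anti-diabetic treatment continues, fasting glucose is checked at least weekly for eight weeks and then at least every two weeks, and the site is to "alert treating physician if FG > 250 mg/dL (8.9 mmol/L". The Grade 3 row has a parallel instruction, and there it reads "alert treating physician if FG>250mg/dl (13.9 mmol/L".

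A separate set of statements concerns which glucose value is taken early in treatment. The note under Table 7-5 (Section 7.2.2.5) says "Fasting plasma glucose at Day 8 and Day 15 of Cycle 1 should be performed both locally and centrally". The body of Section 7.2.2.5 asks for glucose at the same two visits without requiring it to be fasting, and the Table 7-1 row for these visits covers fasting or random values. Section 7.2.2.5.3 says "Beginning with C1D8 until EOT of Core Phase, patients can have RBG testing, at the discretion of the PI". The introductory note to the hyperglycemia rows of Table 6-3 adds "However dose reduction should only be based on FPG", which Section 6.3.2.1.3 puts as a strong recommendation.

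**The concern.** A notification threshold should name one level. This line names two, so the point at which the physician is told depends on the unit in which a site reads its results. The instruction is to alert the treating physician, so the person applying it may be someone else, who would follow the figure as printed and not recognise a slip. In the Extension Phase all laboratory work is local (Section 7.2.2.5), with no central result beside it, so the local unit governs.

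Hyperglycemia is also a common event. It is the most frequent adverse event that Section 1.2.4.2 reports for the phase III alpelisib plus fulvestrant arm, at 65.8% for any grade and 37% for Grade 3 or higher. What is at stake is whether patients in the Grade 2 band are notified consistently while they remain on drug.

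**Working it through.** **Inputs.** All the glucose pairs below come from the protocol, and each ratio is mg/dL divided by mmol/L.

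| Place | mg/dL | mmol/L | Ratio |
|---|---|---|---|
| Table 6-3, Grade 1/2 boundary | 160 | 8.9 | 17.98 |
| Table 6-3, Grade 2/3 boundary and Grade 3 alert | 250 | 13.9 | 17.99 |
| Table 6-3, Grade 3/4 boundary | 500 | 27.8 | 17.99 |
| Inclusion criterion 12 and Table 6-3, Grade 1 | 140 | 7.7 | 18.18 |
| Section 6.3.2.1.3, pre-diabetes, lower limit | 100 | 5.6 | 17.86 |
| Section 6.3.2.1.3, pre-diabetes, upper limit | 125 | 6.9 | 18.12 |
| **Table 6-3, Grade 2 alert** | **250** | **8.9** | **28.09** |

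**Step 1: the protocol's own factor.** Six of the seven pairs give a factor between 17.86 and 18.18, which is 18 apart from rounding. The Grade 2 alert is the only outlier.

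**Step 2: convert each half of the alert line.**
- 250 / 18 = 13.89, that is 13.9 mmol/L, not 8.9.
- 8.9 × 18 = 160.2, that is 160 mg/dL, not 250.

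**Step 3: can rounding explain it?** Take the extremes of the protocol's own factors. 250 mg/dL becomes 250 / 18.18 = 13.75 to 250 / 17.86 = 14.0 mmol/L. 8.9 mmol/L becomes 8.9 × 17.86 = 159.0 to 8.9 × 18.18 = 161.8 mg/dL. Neither range comes near the printed partner.

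**Step 4: size.** 250 − 160 = 90 mg/dL, and 13.9 − 8.9 = 5.0 mmol/L. These are the lower and upper limits of Grade 2, so the two readings are a whole grade band apart.

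**Step 5: what else uses the figure?** In the hyperglycemia rows, the grade limits pair their units consistently, and so do the glucose levels attached to omitting, restarting and permanently discontinuing alpelisib. The Grade 2 dose reduction is tied to failure to return to Grade 1 or better within 21 days, and so to the consistent grade limit. Laboratory toxicity grades are assigned by program from observed values under CTCAE v4.03 (Protocol Section 10.5.2.3; SAP Amendment 4, Section 5.3), without reference to the alert. The primary endpoint and the sample size do not involve glucose.

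**The case against.** The strongest case against the point is that very little depends on this line, and most of that case stands.

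- **Nobody above 250 mg/dL is missed.** A mg/dL site notifies above 250. A mmol/L site notifies above 8.9, which includes everyone above 250. This is correct. It does not make the line harmless, because the two readings still differ for every value between 160 and 250 mg/dL. Which sites then depart from the plan depends on the level the sponsor intended, and the documents do not settle that.
- **The patient is already being managed.** Someone between 160 and 250 mg/dL is Grade 2 at every site, with anti-diabetic treatment started or intensified and glucose checked at least twice weekly until it falls to Grade 1 or better. Table 6-3 also allows local practice for monitoring. This stands: only a notification differs. A reader might take the line for the trigger that escalates treatment, but the table hangs those actions on the grade limits.
- **Random glucose is handled elsewhere.** A reader might infer that random values at Day 8 and Day 15 leave early dose decisions without the fasting value the table calls for. The documents do not support this. For Grades 3 and 4, Table 6-3 has sites confirm fasting status and repeat a non-fasting test within 24 hours. The Grade 2 reduction depends on FPG over 21 days, with fasting checks in the same row. Section 6.3.2.1.3 provides for local fasting glucose. What remains is a wording conflict.
- **Few patients remain.** Enrollment is complete, and the latest count in the protocol is 9 patients on treatment. The prospective reach is small, although dosing in the Extension Phase can run up to 36 months under this table.

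**Conclusion.** The error is certain and narrow. The Grade 2 alert line states two levels about 90 mg/dL (5.0 mmol/L) apart, and the table's own grade limits and Grade 3 alert show that they cannot both be meant. An operative safety threshold is therefore wrong as written, but only a follow-up notification is affected.

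That sites would act at different levels is an inference. It assumes that each site follows the figure in its own unit literally, and the documents report no such divergence.

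A reader might also apply the phase III rate to this trial, 0.658 × 380 = 250, and conclude that about 250 patients fall under the line. The documents do not support that count. The 65.8% is any-grade hyperglycemia, whereas the line sits in the Grade 2 row and the reading changes only where mmol/L is used; neither share is given. Amendments 5 and 6 both list changes to the Grade 2 hyperglycemia text, so Version 06 does not show what most enrolled patients were managed under.

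The fasting or random question is a minor inconsistency of wording. It is mainly retrospective, because enrollment has closed.

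**What to change.** Reconcile the Grade 2 alert line with the table's grade limits and with the Grade 3 alert, so that its mg/dL and mmol/L figures state one glucose level. The sponsor confirms which level was intended; this review takes no position on that.

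At the same time, reconcile the note under Table 7-5 with Table 7-1, the body of Section 7.2.2.5 and Section 7.2.2.5.3 on whether the Cycle 1 Day 8 and Day 15 glucose must be fasting.

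The cost is one corrected figure and one reconciled note, issued by investigator letter or in the next amendment. No analysis, endpoint or sample size changes.

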2.6.3 Risk management strategies

The risk to subjects in this trial will be minimized by compliance with the eligibility criteria and study procedures, close clinical monitoring, recommendations for concomitant medications, guidance for prohibited medications and dose adjustments or interruptions or discontinuations as outlined in Section 6.3. There may be unforeseen risks with alpelisib in combination with fulvestrant or letrozole.

Patients in this study will be carefully monitored for key toxicities that have been observed with alpelisib (see Section 1.2.4) with combination of fulvestrant or letrozole (see Section 1.2.1) with the following assessments (see Section 7): periodic laboratory, renal and liver function, urinallysis and ECG.

Risk will be further minimized by adherence to inclusion/exclusion selection criteria (see Section 5), avoidance of prohibited medication (see Section 6.4.4), close safety monitoring (see Section 8.1) and dose adjustment guidelines (see Section 6.3) for alpelisib and fulvestrant [Faslodex® prescribing information], letrozole prescribing information [Femara® Prescribing Information, Novartis] goserelin and leuprolide [Zoladex® prescribing information] and [Lupron® prescribing information].

A Steering Committee (SC) (see Section 8.7) will be established comprising investigators and Novartis personnel participating in the trial to ensure transparent management of the trial according to the protocol. A Novartis Safety Management Team (SMT) periodically reviews and evaluates all emerging safety data across the alpelisib program for early detection of potential safety signal assessment in a timely manner.

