	 If resolved in ≤ 7 days, then maintain dose level If resolved in > 7 days, then ↓ 1 dose level
Grade 3 (> 3.0 – 6.0 x ULN)	Permanently discontinue patient from alpelisib
Grade 4 (> 6.0 x ULN)	Permanently discontinue patient from alpelisib
Investigations (Hepatic)	
Isolated total Bilirubin elevation	
Grade 1 (> ULN - 1.5 x ULN)	No dose adjustment is required. Initiate appropriate medical therapy and monitor as clinically indicated.
Grade 2 (> 1.5 - 3.0 x ULN)	 Interrupt dose until recovery to Grade ≤ 1 and resume at the same dose if resolved in ≤ 14 days or resume at the next lower dose level if resolved in > 14 days.
Grade 3 (> 3.0 - 10.0 x ULN)	Interrupt dose until recovery to Grade ≤ 1, then resume at the next lower dose level.
Grade 4 (> 10.0 x ULN)	Permanently discontinue.
Isolated AST or ALT Elevation	
Grade 1 (> ULN – 3.0 x ULN)	No dose adjustment is required. Initiate appropriate
Grade 2 (> 3.0 - 5.0 x ULN)	medical therapy and monitor as clinically indicated.
Grade 3 (> 5.0 - 10.0 x ULN)	 Interrupt dose until recovery to Grade ≤ 1, then resume at the next lower dose level.
Grade 4 (> 10.0 x ULN)	Permanently discontinue
Combined elevations of AST or ALT and total Bilirubin	Please see specific instructions in Section 6.3.2.2
Investigations (Gastrointestinal)	
Diarrhea is defined as: A disorder characterized by freq	uent and watery bowel movements.
Colitis is defined as a disorder characterized by inflamm	nation of the colon. (see also Appendix 2)
Grade 1 (Increase of < 4 stools per day over baseline; mild increase in ostomy output compared to baseline) OR	Maintain dose level but initiate appropriate medical therapy and monitor as clinically indicated
Asymptomatic colitis; clinical or diagnostic observations only; intervention not indicated	
Grade 2 (Increase of 4 - 6 stools per day over baseline; moderate increase in ostomy output compared to baseline)	Omit dose until resolved to ≤ Grade 1, initiate appropriate medical therapy then restart at same dose.
limiting instrumental Activities of Daily Living (ADL)	If diarrhea returns as ≥ Grade 2, then omit dose until resolved ≤grade1, then decrease 1 dose level
OR	
Abdominal pain; mucus or blood in stool	Initiate or intensify appropriate medical therapy and monitor as clinically indicated.
	For Grade 2 colitis consider additional treatment, such as steroids.

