14.4 Appendix 4 – Liver event and Laboratory trigger Definitions and Follow-up Requirements

Table 14-5 Liver event and laboratory trigger definitions

	Definition/ threshold
Liver laboratory triggers If ALT, AST and total bilirubin normal at baseline:	· ALT or AST > 5 × ULN · ALP > 2 × ULN (in the absence of known bone pathology) · Total bilirubin > 3 × ULN (in the absence of known Gilbert syndrome) · ALT or AST > 3 × ULN and INR > 1.5 · Potential Hy's Law cases (defined as ALT or AST > 3 × ULN and Total bilirubin > 2 × ULN [mainly conjugated fraction] without notable increase in ALP to > 2 × ULN) · Any clinical event of jaundice (or equivalent term) · ALT or AST > 3 × ULN accompanied by (general) malaise, fatigue, abdominal pain, nausea, or vomiting, or rash with eosinophilia · Any adverse event potentially indicative of a liver toxicity*
If ALT or AST abnormal at baseline:	· ALT or AST > 2x baseline or > 300 U/L (whichever occurs first)

^{*}These events cover the following: hepatic failure, fibrosis and cirrhosis, and other liver damage-related conditions; non-infectious hepatitis; benign, malignant and unspecified liver neoplasms ULN: upper limit of normal

Table 14-6 Follow-up requirements for liver laboratory triggers with liver symptoms

ALT	TBL	Liver Symptoms	Action
ALT increase without b	ALT increase without bilirubin increase:		
If normal at baseline: ALT > 3 x ULN	Normal For participants with	None	· No change to study treatment
If elevated at baseline: ALT > 2 x baseline	Gilbert's syndrome: No change in baseline TBL		· Measure ALT, AST, ALP, GGT, TBIL, INR, albumin, CK, and GLDH in 48-72 hours.
or > 300 U/L (whichever occurs first)			· Follow- up for symptoms.
If normal at baseline: ALT > 5 x ULN for more than two weeks	Normal For participants with Gilbert's syndrome: No	None	· Interrupt study drug · Measure ALT, AST, ALP, GGT, TBIL, INR,
If elevated at baseline: ALT > 3 x baseline or > 300 U/L (whichever occurs	change in baseline TBL		albumin, CK, and GLDH in 48-72 hours. · Follow- up for symptoms.

ALT	TBL	Liver Symptoms	Action
first) for more than two weeks			Initiate close monitoring and workup
If normal at baseline: ALT > 8 x ULN	Normal	None	for competing etiologies.
ALT increase with bilir	ubin increase:		 Study drug can be restarted only if
If normal at baseline: ALT > 3 x ULN	TBL > 2 x ULN (or INR > 1.5)	None	another etiology is identified and liver

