If elevated at baseline: ALT > 2 x baseline or > 300 U/L (whichever occurs first)	For participants with Gilbert's syndrome: Doubling of direct bilirubin		enzymes return to baseline.
If normal at baseline: ALT > 3 x ULN	Normal or elevated	Severe fatigue, nausea, vomiting, right	
If elevated at baseline: ALT > 2 x baseline or > 300 U/L (whichever occurs first)		upper quadrant pain	

Table 14-7 Follow-up requirements for liver laboratory triggers

Criteria	Actions required	Follow- up monitoring
Total Bilirubin (isolated)		
>1.5 – 3.0 ULN	Maintain treatment Repeat LFTs within 48-72 hours	Monitor LFTs weekly until resolution ^c to ≤ Grade 1 or to baseline
> 3 - 10 × ULN (in the absence of known Gilbert syndrome)	Interrupt treatment Repeat LFT within 48-72 hours Hospitalize if clinically appropriate Establish causality Record the AE and contributing factors (e.g. conmeds, med hx, lab) in the appropriate CRF	Monitor LFTs weekly until resolution ^c to ≤ Grade 1 or to baseline (ALT, AST, total bilirubin, Alb, PT/INR, ALP and GGT) Test for hemolysis (e.g. reticulocytes, haptoglobin, unconjugated [indirect] bilirubin)
> 10 x ULN	Discontinue the study treatment immediately Hospitalize the participant Establish causality Record the AE and contributing factors(e.g. conmeds, med hx, lab) in the appropriate CRF	ALT, AST, total bilirubin, Alb, PT/INR, ALP and GGT until resolution ^c (frequency at investigator discretion)

Criteria	Actions required	Follow- up monitoring
Any AE potentially indicative of a liver toxicity*	Consider study treatment interruption or discontinuation Hospitalization if clinically appropriate Establish causality Record the AE and contributing factors (e.g., conmeds, med hx, lab) in the appropriate CRF	Investigator discretion

^aElevated ALT/AST > 3 × ULN and TBL > 2 × ULN but without notable increase in ALP to > 2 × ULN ^b(General) malaise, fatigue, abdominal pain, nausea, or vomiting, or rash with eosinophilia ^cResolution is defined as an outcome of one of the following: (1) return to baseline values, (2) stable values at three subsequent monitoring visits at least 2 weeks apart, (3) remain at elevated level after a maximum of 6 months, (4) liver transplantation, and (5) death.

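### Table 6-3 and Appendix 4 of the protocol give opposite alpelisib instructions for two isolated liver findings, and the Table 6-3 bilirubin row has no restart route for a patient who worsens and then returns to a raised baseline

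*Protocol*

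**What the plan says.** Dosing rules for liver findings appear in two places in the protocol.

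- **Section 6.3.1.4, Table 6-3.** For isolated bilirubin Grade 2 (above 1.5 to 3.0xULN) the instruction is "Interrupt dose until recovery to Grade ≤ 1 and resume at the same dose if resolved in ≤ 14 days", with the next lower dose if recovery takes longer. For isolated AST or ALT Grade 3 (above 5.0 to 10.0xULN) it is "Interrupt dose until recovery to Grade ≤ 1, then resume at the next lower dose level". Neither row sets a minimum duration before the hold.
- **Section 14.4 (Appendix 4), Table 14-7.** For isolated bilirubin above 1.5 to 3.0xULN the required action is "Maintain treatment Repeat LFTs within 48-72 hours".
- **Section 14.4, Table 14-6.** For ALT above 3xULN from a normal baseline, with normal bilirubin and no symptoms, the action is "No change to study treatment". Interruption begins at "ALT > 5 x ULN for more than two weeks", or without a duration condition at "If normal at baseline: ALT > 8 x ULN".

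Section 2.6.3 refers readers to "dose adjustments or interruptions or discontinuations as outlined in Section 6.3". Sections 6.1.4, 6.3.3 and 7.1.5 also point to Section 6.3, and Section 6.3.1.4 itself points to Table 6-3. Section 6.3.1.4 adds that alpelisib held for more than 28 days must be stopped permanently.

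Inclusion criterion 10 (Section 5.2) admits total bilirubin below 2xULN. With Gilbert's syndrome it admits total bilirubin below 3.0xULN or direct bilirubin below 1.5xULN.

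**The concern.** A site that opens Appendix 4 for a liver result may keep dosing where Table 6-3 tells it to hold. No sentence in the protocol says which table prevails. The labels do not settle it either: Section 6.3.1.4 presents the Table 6-3 interruptions as recommendations to be applied with clinical judgment, while the Table 14-7 column is headed as required actions.

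The bilirubin row of Table 6-3 raises a further problem. It ends a hold only at Grade 1 or better, yet the entry criteria admit patients whose usual bilirubin is already above the Grade 1 ceiling of 1.5xULN. For them, full recovery to baseline does not count as recovery, and the 28-day rule could then end alpelisib although the liver test is back where it started.

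**Working it through.** No figure in the plan needs reproducing. The check sets the two sources side by side.

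**Isolated total bilirubin**

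| Range | Table 6-3 | Table 14-7 |
|---|---|---|
| >1.5 to 3.0xULN | interrupt | maintain |
| >3 to 10xULN | interrupt | interrupt (no known Gilbert syndrome) |
| >10xULN | discontinue | discontinue |

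The first range has the same limits in both tables and opposite actions.

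**Isolated ALT (normal baseline, normal bilirubin, no symptoms)**

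| Range | Table 6-3 | Table 14-6 |
|---|---|---|
| >3 to 5xULN | no adjustment | no change |
| >5 to 8xULN, up to two weeks | interrupt | no change |
| >5 to 8xULN, more than two weeks | interrupt | interrupt |
| >8 to 10xULN | interrupt | interrupt |

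Table 14-6 does not print the second range as a row of its own. It follows from the other rows: such a value is above 3xULN, so the no-change row applies, and it meets neither interruption condition. Table 14-6 lists ALT only, so the comparison says nothing about AST.

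**Baseline bilirubin against the Table 6-3 Grade 2 row**

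The row spans 3.0 − 1.5 = 1.5xULN. Criterion 10 admits baselines inside it:

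- without Gilbert's syndrome, from above 1.5 to below 2.0xULN, a width of 2.0 − 1.5 = 0.5xULN;
- with Gilbert's syndrome, on the total-bilirubin limit, from above 1.5 to below 3.0xULN, essentially the whole row.

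As an illustration with assumed values, a patient enters at 1.8xULN, rises to 2.5, is held, and returns to 1.8. Since 1.8 > 1.5, Grade 1 is not reached. Both restart branches of the row (up to 14 days and beyond 14 days) require Grade 1, so the hold continues past 28 days and permanent discontinuation follows.

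The protocol uses baseline elsewhere. Table 14-7 accepts Grade 1 or baseline as the end of bilirubin monitoring, and Table 6-3 itself resolves amylase and lipase elevations to baseline. The baseline-adjusted thresholds in Section 6.3.2.2 cover only combined transaminase and bilirubin elevations, so they do not help this row.

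**Glucose alert**

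The Grade 2 heading in Table 6-3 pairs 160 mg/dL with 8.9 mmol/L and 250 mg/dL with 13.9 mmol/L. The alert in the Grade 2 row pairs 250 mg/dL with 8.9. The two printed limits therefore differ by 250 − 160 = 90 mg/dL. The Grade 3 alert has the correct pair.

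**The case against.** The strongest reply is that precedence is clear in practice. Every dosing pointer in the body leads to Section 6.3, and no body text sends a site to Appendix 4 for liver findings, whereas the diarrhea and stomatitis rows of Table 6-3 do cite their appendices. The table titles also divide the work: Table 6-3 covers interruption and restart, and Tables 14-6 and 14-7 cover follow-up. This stands as far as it goes. It makes Table 6-3 the likely governing source and lowers the risk. It does not remove treatment actions printed in Appendix 4 that say the opposite.

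It is also fair to say that the ALT conflict is derived by reading rows together and is confined to the conditions stated above. The derivation is short, and no other row of Table 14-6 covers that case.

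A reader might infer three stronger things that the documents do not support.

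- **That a stable, unchanged raised baseline bilirubin itself triggers a hold and then discontinuation.** Section 6.3.1.4 bases dose changes on toxicity in the management of adverse reactions, and Section 8.1.1 defines an adverse event as something that appears or worsens. An unchanged admitted value does not clearly start a hold. The gap concerns the patient who worsens and then recovers to baseline.
- **That the tables also conflict above 10xULN for ALT.** Table 14-6 has no separate row there, but Section 6.3.1.4 says treatment must be discontinued where Table 6-3 indicates it, which settles the case.
- **That the restart rules for isolated ALT conflict.** The Table 14-6 cell beginning "Study drug can be restarted only if" is split in the extracted text, so its reach across rows should be checked in the PDF. It is not relied on here.

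**Conclusion.** The point holds and is minor. Two instructions conflict in current text: isolated bilirubin above 1.5 to 3.0xULN, where the conflict is printed directly, and isolated ALT above 5 to 8xULN for up to two weeks, where it follows from reading the rows together. Table 6-3 also lacks a restart route for a patient who worsens and returns to a baseline above 1.5xULN. The glucose pairing is a separate unit error. In mmol/L it makes the alert fire early, and it changes no dose.

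The documents give no count of patients in the affected ranges, so no frequency can be stated. Remaining exposure is small. The Amendment 6 summary reports enrollment complete and 9 patients on treatment at 30-Jan-2022, and Section 7.1.4 makes Extension Phase chemistry a matter of clinical indication. No endpoint, hypothesis test or planned analysis is affected.

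The conclusion assumes that the extracted rows of Tables 6-3, 14-6 and 14-7 match the PDF, apart from the restart cell set aside above.

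**What to change.** 1. State in Section 6.3.1.4 and in Appendix 4 that Table 6-3 governs alpelisib interruption, reduction, discontinuation and restart, and that Appendix 4 governs laboratory monitoring and work-up.
2. Align the Table 14-7 row for isolated bilirubin above 1.5 to 3.0xULN, and the Table 14-6 rows that cover isolated ALT above 5 to 8xULN, with Table 6-3. Check the Table 14-6 restart condition in the PDF at the same time.
3. After medical confirmation, let the Table 6-3 Grade 2 bilirubin row resolve to Grade 1 or baseline for patients with Gilbert's syndrome or raised baseline bilirubin.
4. Change 8.9 to 13.9 mmol/L in the Grade 2 glucose alert.

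The cost is one clarification letter to sites or a few lines in an amendment. There is no data or analysis cost.
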